9.2.2. Data Coding

AE coding and coding of concomitant diseases will be performed according to MedDRA Version 13.0 or higher. Concomitant medication will be coded using the ATC code.

9.2.3. Database Lock

The database will be only locked after the following requirements are fulfilled:

- All data have been entered in the database
- Decisions on how individual protocol violations are to be dealt with have been agreed upon
- Written authorisation from the project leader of trial at advanceCOR GmbH has

been granted

9.3. Statistical Procedures

Safety

The number and proportion of patients experiencing each type of event will be summarised per treatment group. Only treatment-emergent events will be included in the analysis (i.e. those that began or worsened after screening (visit 1)).

The incidence and event (or event grouping) will be summarised and compared between treatment groups using Pearson's chi-squared tests.

Blind Review/Final Statistical Analysis Plan

A blinded review of the data shall be performed within the framework of the requirements of the ICH Guideline E9. The Blind Review Report will include the final statistical analysis plan (updated statistical analysis plan) and the final definition of data sets. If the blind review suggests changes to the principal features stated in the protocol, these should be documented in a protocol amendment.

The Blind Review Report will be finalised before the blind will be broken. Formal records shall be kept of when the statistical analysis plan was finalised as well as when the blind was subsequently broken.

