
Title of study:
 
Revacept, an inhibitor of platelet adhesion in symptomatic carotid stenosis: A phase II, multicentre, randomised, dose-finding, double-blind and placebo-controlled superiority study with parallel groups.
	

Protocol identification (code or number):
 
Revacept/CS/02
	

OBJECTIVES
 
Efficacy objectives are:
 
 • Assessment of incidence of microembolic signals (MES) by transcranial Doppler (TCD) examination (before and after treatment) • Rate of MES per hour (before and after treatment) • Cerebral lesion analysis by DWI-NMR • Assessment of neurological status (NIH Stroke Scale) • Clinical endpoints will be summarised cumulatively i.e. before treatment, after treatment, at 3 months and at 12 months. The following endpoints will be recorded: 
 ○ Rate of all cause death ○ Rate of stroke-related death ○ Any TIA, amaurosis fugax or stroke including haemorrhagic stroke • Assessment of cardiovascular outcome including myocardial infarction and re-intervention up to 3 and 12 months 	

Safety objectives are to investigate whether Revacept compared to placebo induces adverse and serious adverse events.

Haemostasis will be closely monitored by assessing:

- laboratory parameters indicating thrombocytopenia and bleeding according to the RE-LY study group criteria
- where feasible: in vitro platelet function with collagen, TRAP and ADP-mediated platelet aggregation and in vitro bleeding time by PFA-100 / PFA-200

Pharmacokinetics of Revacept with respect to drug interaction with other antiplatelet drugs will also be assessed by determining plasma concentrations at various time points after administration of study medication for approximately 20 % of patients.

Methodology:

Multicentre, randomised 2:1, double-blind, placebo controlled, parallel groups, analysis. Blinded evaluation of efficacy and safety endpoints.

Treatment Regime:

Patients suffering from symptomatic carotid artery stenosis, transient ischemic attacks (TIAs), amaurosis fugax or stroke receive either Revacept (single dose) plus antiplatelet monotherapy (Aspirin or Clopidogrel) or monotherapy alone.

Patients receive a single dose of trial medication by intravenous infusion for 20 minutes. Patients are followed up one and three days after treatment, at 3 months and by a telephone interview at 12 months.

Treatment Groups:

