1.3. Data Safety Monitoring Board

The Data Safety Monitoring Board (DSMB) will consist of a statistician together with two independent neurologists who are scientifically well qualified, and who have personal experience of large multicentre studies and data monitoring activities.

Chairman:

[name]. med. [name]
[name]
[name]
[contact]
[contact]

Members:

[name]. [name]
[name]
[name]
[contact]
[contact]

[name]. rer. nat. [name]
[name]
[name]
[contact]
[contact]

The DSMB will hold regular meetings to review data concerning safety, efficacy and study performance. Unblinded data describing clinical endpoints, adverse events and laboratory values are to be compiled for these meetings by d.s.h. statistical services. The DSMB will

inform and advise the sponsor of all findings with regard to safety, efficacy and study performance. Review of data can lead the DSMB to a recommendation to the sponsor to stop the study. Minutes of Committee meetings will be recorded and filed. A special charter for the DSMB evaluation will be available. In accordance to GCP-V §13, SUSARS will be reported to the ethics committee, regulatory authority and the DSMB. If serious adverse events are more common in the experimental arm compared to the control arm the risk/benefit consideration will be reassessed. The Committee will inform the sponsor in writing if the frequency of serious adverse events including deaths exceeds 8 percent in one of the groups, and will advise concerning appropriate actions.

The first safety analysis will be performed by the DSMB once 10 patients have completed visit 5. The first 10 patients will be treated sequentially, e.g. only one patient is randomised at a time. The next patient will be randomised only once the first patient has completed visit 5 and no suspected unexpected serious adverse event has occurred (see also section 5.1). In addition, patient randomisation will be stopped by advanceCOR each time a serious adverse event occurs which is unexpected and possibly related to the study medication (SUSAR, see also section 8.3.2). Patient randomization will be resumed only if recommended by the DSMB. Thereafter, the DSMB will perform safety analysis at least annually.

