Following these encouraging preclinical studies, safety and tolerability of Revacept was investigated in a first-in-man study (Ungerer et al., 2011). In a phase I clinical trial, 30 male human volunteers received a single intravenous dose of Revacept ranging between 10-160 mg. All investigated doses were well tolerated and no drug-related side effects occurred. Moreover, no anti-Revacept antibodies were produced and favourable pharmacokinetic and pharmacodynamic profiles were observed. In summary, results from both preclinical studies and the phase I clinical trial constitute a solid basis for proceeding to a clinical trial in the target patient population. The study presented here aims to demonstrate both safety and evidence of efficacy of Revacept treatment in patients suffering from symptomatic carotid stenosis.

Dose selection rationale

Detailed background information on preclinical pharmacology, pharmacokinetics, toxicology and on the phase I clinical study of Revacept is provided in the Investigator Brochure. When 10 – 160 mg Revacept were administered during a phase I clinical trial, maximal pharmacodynamic effects were measured *ex vivo*, starting at 40 mg, and no drug-related adverse events occurred. Pharmacokinetic studies demonstrated that the area under the curve and maximum concentration proportionally increased with higher dose levels. Because no maximum tolerated dose (MTD) was defined for the adult population and with data generated during preclinical and phase I studies we propose that maximal therapeutic effect is achieved with low to medium doses of Revacept (40 mg and 120 mg).

Overall risk/benefit assessment

Revacept is a novel therapeutic agent that potently inhibits platelet aggregation at the site of atherosclerotic plaques without compromising systemic coagulation in animal models and healthy volunteers. No toxicities were observed during preclinical studies and no adverse reactions were observed when Revacept was administered to healthy human volunteers. Consequently, safety concerns are limited to adverse reactions specific to the target patient population and rare side effects.

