## **3.3 Sample size**

Primary sample size estimation was conducted based on the CARESS study results (Markus et al., 2005). 50 patients should be allocated to each treatment arm. Due to low incidence of MES (high screening failure rates) study design was changed to exploratory study (Version 8 of the study protocol).

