### 7.6 General Calculation Rules

Binary, categorical and ordinal parameters will be summarised by means of absolute and percentage numbers (including 'missing data' as valid category at visit 1). Numerical data will be

summarised by means of standard statistics (i.e. number of available data, mean, standard deviation, minimum, median, maximum, lower and upper quartile). Wherever useful, the summary statistics will be presented by stratification according to centers and/or visit. In addition, adequate figures (e.g. bar charts, Box-Whisker-Plots) will be presented to summarise the results for some parameters.

All statistical tests will be performed two-sided and will be interpreted in a descriptive-exploratory way. Two-sided confidence intervals (CIs) will be displayed for important variables. Appropriate methods will be used to derive confidence intervals, depending on data nature and distribution. All safety and tolerability data will be presented in a purely descriptive manner as outlined below.

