### **8.5 Assessment of safety**

Safety outcome between groups and between placebo and the combined Revacept groups will be compared.

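### Adverse events are compared by Pearson p-value with no risk difference or interval for any safety outcome, and the documents disagree on whether safety is tested

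*Protocol*

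**What the plan says.** - **Method for adverse events.** Protocol 9.3 asks for numbers and proportions per group, and then: "The incidence and event (or event grouping) will be summarised and compared between treatment groups using Pearson's chi-squared tests".
- **Pooled comparison.** SAP 8.5: "Safety outcome between groups and between placebo and the combined Revacept groups will be compared". No test, estimate or interval is named there, and SAP 8.5.4 (adverse events) lists only summaries and frequency tables.
- **Size.** SAP 3.3: "50 patients should be allocated to each treatment arm". The pooled comparison is therefore 100 v 50, in line with the 2:1 ratio in the synopsis.
- **Status of the safety analysis.** The protocol synopsis excludes formal hypothesis testing and promises descriptive summaries. Protocol 9.3 tests. SAP 7.6 says "All safety and tolerability data will be presented in a purely descriptive manner as outlined below". SAP 8.5 orders comparisons, 8.5.1 applies Wilcoxon tests to changes in vital signs, and 8.5.5 expects p-values for laboratory and bleeding data, to be read exploratively.
- **Intervals.** SAP 8.4.1 specifies a risk difference with 95% interval for every MES group comparison. SAP 7.6 promises intervals for important variables without naming any, and protocol 9.3.2 mentions them for efficacy data only.
- **Aim.** Protocol section 2 says the study "aims to demonstrate both safety and evidence of efficacy of Revacept treatment".

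**The concern.** The safety objective in the synopsis is comparative: Revacept against placebo for adverse and serious adverse events. For that comparison the protocol names a p-value and no measure of how large a difference the data still allow. The risks the protocol itself discusses, such as bleeding, platelet effects and allergic reactions, may well be uncommon. In groups of 50 a non-significant result is then the likely outcome whether or not there is harm, and a chi-squared test on a handful of events is unreliable. A report that follows the plan could state that no significant difference was found while the data remain compatible with a material excess. The disagreement between sections also leaves the choice of safety method open until the data are in hand.

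**Working it through.** **Inputs.** 50 per arm and 100 v 50 pooled come from the documents. The documents give no expected SAE rate, no safety alpha and no safety power, so there is no planned figure to reproduce. Assumptions: two-sided 5%, uncorrected Pearson test. The 8% control rate is also an assumption. It is borrowed only for scale from protocol 1.3, where the DSMB writes to the sponsor if "the frequency of serious adverse events including deaths exceeds 8 percent in one of the groups".

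**1. Chance of flagging a doubling, 8% to 16%, 50 v 50.** Normal approximation: power = Φ[(Δ - 1.96·√(2·p̄·q̄/n)) / √((p₁q₁ + p₂q₂)/n)].

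With p̄ = 0.12: 2·p̄·q̄ = 0.2112 and p₁q₁ + p₂q₂ = 0.0736 + 0.1344 = 0.208. So (0.08 - 1.96·0.0650)/0.0645 = -0.73, and Φ = 23.1%. Summing exact binomial probabilities over all tables with chi-squared of at least 3.84 in the direction of harm gives 24.1%. The same sum at 100 v 50 gives 26.2%.

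Exact chance of flagging a doubling at other control rates:

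| Control rate | 50 v 50 | 100 v 50 |
|---|---|---|
| 2% | 5% | 2% |
| 4% | 12% | 10% |
| 8% | 24% | 26% |
| 15% | 44% | 54% |
| 20% | 60% | 71% |
| 30% | 88% | 95% |

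The share missed runs from about 95-98% at a 2% control rate to about 5-12% at 30%.

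**2. Rare events, if Pearson's test were used at 100 v 50.** Chi-squared = N(ad - bc)² / product of the four margins.

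- 0/100 v 2/50: 150·200²/(100·50·2·148) = 4.05, p = 0.044 in Revacept's favour (Fisher p = 0.11).
- 7/100 v 0/50: 150·350²/(100·50·7·143) = 3.67, p = 0.055.
- 8/100 v 0/50: 150·400²/(100·50·8·142) = 4.23, p = 0.040 (Fisher p = 0.052).

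Exact chance of a flag with equal true rates:

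| True rate in both groups | Favours Revacept | Signals harm |
|---|---|---|
| 1% | 3.3% | <0.001% |
| 2% | 4.1% | 0.03% |
| 3% | 3.5% | 0.23% |
| 4% | 3.1% | 0.64% |
| 8% | 2.8% | 1.8% |

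With real harm (placebo v Revacept), favour/harm flags are 1.2%/0.06% at 1% v 2%, 0.6%/1.8% at 2% v 4%, and 0.2%/2.9% at 1% v 4%.

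**3. What an interval would show.** Newcombe: with d the difference and l, u the Wilson limits (1 = Revacept, 2 = placebo), lower = d - √((p₁-l₁)² + (u₂-p₂)²) and upper = d + √((u₁-p₁)² + (p₂-l₂)²). In percentage points:

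- 0/100 (0 to 3.70) v 2/50 (1.10 to 13.46): -4 - 9.46 = -13.5, and -4 + √(3.70² + 2.90²) = +0.7.
- 7/100 (3.43 to 13.75) v 0/50 (0 to 7.13): 7 - √(3.57² + 7.13²) = -1.0, and 7 + 6.75 = +13.7 (unrounded 13.75).
- 8/100 (4.11 to 15.00) v 4/50 (3.15 to 18.84): 0 - √(3.89² + 10.84²) = -11.5, and √(7.00² + 4.85²) = +8.5.

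In the first table the p-value suggests protection, and in the second it dismisses an excess. The interval shows that zero is still possible in both, and how much harm remains possible.

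**The case against.** The strongest reply is that the study is openly exploratory. SAP 7.6 makes all tests descriptive-exploratory and 8.5.5 says so again for laboratory and bleeding p-values. Low power for uncommon harms comes with 150 patients: 80% power for 8% v 16% needs [(1.96·0.4596 + 0.842·0.4561)/0.08]², about 258 per arm. Much of this stands, and it rules out four stronger readings.

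- **That safety is to be proved by non-significance.** A reader might infer this from *demonstrate* in the introduction. That is one sentence. The synopsis speaks of investigating, section 3 of assessing, and no section treats p > 0.05 as proof of safety.
- **That p-values are the only safety evidence.** Protocol 9.3 and 9.3.5 and SAP 8.5.4 and 8.7 plan frequency tables, intensity, relatedness and listings. The DSMB reviews unblinded data. A large excess would be visible in the counts. What is missing is a planned estimate of the difference with its uncertainty.
- **That three of four doublings are missed.** This holds only near an 8% control rate, which is a notification trigger and not a planning rate.
- **That the pooled test flags almost only in Revacept's favour.** Neither document applies Pearson's test to the pooled comparison. The SAP says it details the analyses outlined in the protocol, so carrying the test over is a possible reading. Yet where the SAP names a test for a pooled comparison (8.4.1), it is Fisher's. The lopsidedness also needs equal true rates of about 3% or less. It fades from 4% upward and reverses when harm is real and larger, as at 2% v 4%.

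The exploratory label does not answer the remaining point: a p-value from two events, or a bare statement of no significant difference, misinforms a reader in an exploratory report too.

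**Conclusion.** The point holds in a limited form. The protocol's stated comparison for adverse events is a p-value, no safety outcome is assigned a risk difference or interval, and the sections disagree on whether safety is tested. At an assumed 8% control rate, a doubling is flagged in only 24-26% of trials. At other rates the figure runs from 2-5% (control 2%) to 88-95% (control 30%). The rare-event behaviour at 100 v 50 is conditional on Pearson's test being used there. All figures assume a two-sided 5% level and the planned 50 per arm; the number actually randomised is not in the documents. This is a weakness in what the safety tables will be able to say. It does not show that the plan rests a claim of safety on a non-significant test.

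**What to change.** 1. In protocol 9.3 and SAP 8.5, make the risk difference with a two-sided 95% Newcombe interval the safety comparison, for each dose against placebo and combined Revacept against placebo. Cover at least any SAE, any bleeding, major bleeding (protocol 7.2.11) and thrombocytopenia. Add the same interval to the Fisher comparison of stroke/TIA in SAP 8.4.5.
2. Drop the Pearson tests. Any p-value that is kept should be secondary and from Fisher's exact test. Fisher is not a cure: for 8% v 16% at 50 v 50 its power is 14% against 24%, and at equal 2% rates in the pooled comparison it still flags 1.6% in Revacept's favour against 0.007% for harm. A score interval that inverts the Pearson statistic would inherit the 0.044 result, so name Newcombe.
3. State that p > 0.05 is not evidence of safety, and that the safety statement rests on the interval and its upper limit.
4. Reconcile SAP 7.6 with 8.5, 8.5.1 and 8.5.5, and all of these with the protocol synopsis and 9.3.
5. In protocol section 2, replace *demonstrate* with *estimate* or *assess* for safety.

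**Cost.** Wording changes and a few extra table columns, with no new patients or data. The intervals will be visibly wide: identical 8% rates (8/100 v 4/50) still allow an excess of 8.5 points. The safety conclusion becomes more modest as a result.

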9.3.1. Definition of Populations

Before study unblinding or data review, possible protocol violations will be classified as "major", "minor", or "none". Subjects will be allocated to the individual data sets with regard to the classification of possible protocol violations. The final data sets shall be described in detail in the Blind Review Report.

Safety Populations

All Subjects who have received study medication and have had one contact with the Investigator afterwards are analysed for safety.

ITT Population (Full Analysis Set)

For efficacy, all subjects who have had at least one dose of medication will be included in the ITT analysis. The ITT analysis is defined as the first line efficacy analysis.

Per-Protocol (PP) Population

The PP population includes all subjects who are eligible for ITT evaluation and who, in addition, do not show major protocol deviations.

9.3.2. Multicentre Analysis

The analysis of combined centers is the primary analysis of efficacy endpoints. Individual center results will be presented in a graphical overview with effect sizes and confidence intervals for efficacy data.

9.3.3. Missing Values

Rules on how missing values of efficacy variables will be replaced are to be described in the Statistical Analysis Plan.

9.3.4. Software

Data analysis will be performed in a validated working environment in compliance with the

requirements of the ICH-Guidelines E9 [1998]. The software to be used for data evaluation will be described in the statistical analysis plan.

9.3.5. Safety Analysis

Physical examinations and vital signs

Findings of physical examinations and changes in vital signs (blood pressure and heart rate) and body weight from baseline will be presented with descriptive statistics.

Adverse events

Adverse events (AEs) will be categorised by primary system organ class (SOC) and MedDRA preferred term as coded using the MedDRA dictionary. The number, intensity, relation to study medication and action taken will be described by frequency tables. Serious adverse events will be discussed separately.

Laboratory variables

Laboratory variables will be presented as:

- Tables with raw values ("data as available") and descriptive statistics with markings of values outside reference range and
- Tables with changes from baseline and with descriptive statistics.

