As for all antiplatelet drugs, it cannot be entirely excluded at this stage of development that Revacept could potentially increase bleeding propensity. Especially the likelihood of bleeding problems might occur in combination with multiple anti-thrombotic or antiplatelet drugs. In order to keep this risk low, concomitant oral anticoagulation and antiplatelet drugs other than anti-thrombotic monotherapy with Aspirin or Clopidogrel are prohibited in this study.

The immunogenicity of Revacept is judged to be considerably low, as its components are naturally occurring in the human body and should hence be recognised as 'self'. As for all therapeutic proteins, there is residual risk for Revacept triggering an aberrant immune reaction. Potential allergic responses may produce mild symptoms such as skin rashes and flue-like symptoms but also severe and potentially life-threatening reactions such as anaphylactic shocks. In order to minimise the risk of acute allergic reactions, patients with a history of allergic responses to intravenously administered drugs will be excluded from study participation. Furthermore, all patients will remain under medical supervision for 24 hours after receiving study medication.

Although the risk for production of anti-drug antibodies is low for single dose application, anti-Revacept autoantibodies could potentially cross-react with circulating platelets. For minimisation of this risk, patients with a known history of thrombocytopenia will not be

allowed to participate in this study. Furthermore, platelet counts and bleeding time will be closely monitored throughout the trial and blood samples for determination of anti-drug antibodies will be collected before and 3 months after exposure to study treatment.

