3. STUDY ENDPOINTS

The **efficacy endpoints** are:

- to evaluate whether the incidence of preoperative microembolic signals (MES) is reduced in patients with symptomatic carotid artery stenosis who have been treated with Revacept plus antiplatelet monotherapy (aspirin or clopidogrel) versus antiplatelet monotherapy alone (placebo). MES will be assessed by transcranial Doppler (TCD) examination.(before and after treatment)
- Rate of MES per hour (before and after treatment)
- Assessment of neurological status (NIH Stroke Scale)
- Cerebral lesion analysis by DWI-NMR and correlation to neurological status (before and after treatment)
- Clinical endpoints will be summarised cumulatively i.e. before treatment, one and three days after treatment, at 3 months and at 12 months. The following endpoints will be recorded:
 - Rate of all cause death
 - Rate of stroke-related death
 - Any TIA, amaurosis fugax or stroke including haemorrhagic stroke
- Assessment of cardiovascular outcome including myocardial infarction and re-intervention up to 3 and 12 months

Safety objectives

To assess safety, adverse events will be continuously recorded and be overseen by an independent Data Safety Monitoring Board (see section 1.3).

Safety will be summarised by treatment group and include the following:

- Vital signs
- ECG parameters
- Anti-drug antibody titres
- Reporting AEs including wound healing complications, laboratory abnormalities and use of concomitant medication
- Haemostasis will be closely monitored by assessing:
 - laboratory parameters indicating thrombocytopenia and bleeding according to the RE-LY study group criteria
 - where feasible: in vitro platelet function with collagen, TRAP and ADP-mediated platelet aggregation and in vitro bleeding time by PFA-100 / PFA-200

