5.2.2. Exclusion Criteria

Subjects must not be included for any of the following reasons:

1) Sex and reproductive Status:

- WOCBP who are unwilling or unable to use an acceptable method to avoid pregnancy for up to 4 weeks after receiving investigational product.
- Women who are pregnant or breastfeeding
- Women with a positive pregnancy test on enrolment or prior to investigational product administration.

2) Target disease exceptions

- NIHSS score > 18
- Recent intracerebral haemorrhage by X-ray computed tomography (CT) or nuclear magnetic resonance (NMR)
- Cardiac cause of embolisation (atrial fibrillation or other cardiac source e.g. artificial

heart valves)

3) Medical history and concurrent disease

- History of hypersensitivity, contraindication or serious adverse reaction to inhibitors of platelet aggregation, hypersensitivity to related drugs (cross-allergy) or to any of the excipients in the study drug
- History or evidence of thrombocytopenia ($<30.000/\mu\text{l}$), bleeding diathesis or coagulopathy (pathological international normalised ratio (INR) or activated partial thromboplastin time (aPTT))
- Thrombolysis within the last 48 hours
- Relevant haemorrhagic transformation as determined by CT, NMR or anamnesis
- Oral anticoagulation or dual anti-platelet therapy with aspirin or clopidogrel and other P2Y inhibitors at screening (3 days for dipyridamole extended release; 8 hours for tirofiban/Aggrastat)
- Sustained hypertension (systolic BP >179 mmHg or diastolic BP >109 mmHg), hypertensive patients shall be treated in accordance with current guidelines for the management of arterial hypertension
- History of severe systemic disease such as terminal carcinoma, renal failure (or current creatinine >200 $\mu\text{mol/l}$), cirrhosis, severe dementia, or psychosis
- Current severe liver dysfunction (transaminase level greater than 5-fold over upper normal range limit)
- Active autoimmune disorder such as systemic lupus erythematosus, rheumatoid arthritis, vasculitis or glomerulonephritis
- Known atrial fibrillation or other clinically significant ECG abnormalities (at present)

4) Other Exclusion criteria

- Inability to provide informed consent (except for patient's legally responsible representative)
- Acoustic window that does not allow for TCD recording
- Participation in any other interventional study within less than 30 days prior to screening
- Suspected poor capability to follow instructions and cooperate

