### 4.2 Safety endpoints:

- Vital signs
- ECG parameters
- Anti-drug antibody titres
- Reporting AEs including wound healing complications, laboratory abnormalities and use of concomitant medication
- Haemostasis will be closely monitored by assessing:
  - laboratory parameters indicating thrombocytopenia and bleeding according to the RELY study group criteria
  - where feasible: in vitro platelet function with collagen, TRAP and ADP-mediated platelet aggregation and in vitro bleeding time by PFA-100 / PFA-200

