#### **8.5.5 Laboratory results**

The following endpoints will be evaluated exploratory using descriptive methods of statistics. Generated p-values will be interpreted in an explorative way.

- Laboratory results
  - Biochemistry
  - Haematology
  - Coagulation
  - Urinalysis
- Bleeding

- Reduction in haemoglobin level
  - by at least 20 g/L
  - by at least 50 g/L
  - of  $\geq 2$  units of blood
  - of  $\geq 4$  units of blood
- Requiring transfusion
  - of  $\geq 2$  units of blood
  - of  $\geq 4$  units of blood
- Symptomatic bleeding in a critical area of organ
  - Intra-ocular
  - Intra-spiral
  - Intra-musculär
  - Retro-peritoneal
  - Intra-articular
  - Pericardial
  - Subdural intra-cranial
  - Intra-cerebral
- Other symptomatic bleeding
  - Gastrointestinal
  - Other organ
- Involving hypotension
- Surgery necessary
- Fatal

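### Thrombocytopenia is a named safety endpoint, but neither document defines an on-study laboratory case or plans a per-arm count of patients meeting a platelet criterion

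*Protocol*

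**What the plan says.** The endpoint is set in protocol section 3: "laboratory parameters indicating thrombocytopenia and bleeding according to the RE-LY study group criteria". SAP section 4.2 repeats it: "laboratory parameters indicating thrombocytopenia and bleeding according to the RELY study group criteria". Neither attaches a platelet count, a grade or a percentage fall.

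Protocol section 2 explains why platelets are of interest for this product. It rates the antibody risk after a single dose as low, but notes that "anti-Revacept autoantibodies could potentially cross-react with circulating platelets", and undertakes to follow platelet counts closely.

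The planned laboratory outputs are:

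- Protocol section 9.3.5: raw values and "descriptive statistics with markings of values outside reference range", plus "Tables with changes from baseline and with descriptive statistics".
- SAP section 8.5.5, for haematology among other groups: "The following endpoints will be evaluated exploratory using descriptive methods of statistics". Exploratory p-values are mentioned, but no test is named.

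The bleeding part of the same endpoint is treated differently. SAP section 8.5.5 lists "Reduction in haemoglobin level" with cut-offs of 20 and 50 g/L, and transfusion categories of 2 and 4 units.

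The only platelet threshold in either document is the eligibility rule in protocol section 5.2.2, "History or evidence of thrombocytopenia", set at 30.000/µl. It is not used as an on-study event definition.

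**The concern.** An endpoint that is named but has no derived variable leaves the report without a direct answer to a simple question: how many patients in each arm became thrombocytopenic after dosing?

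An antibody-mediated effect would plausibly appear as a marked fall in a few patients rather than a small fall in everyone. That pattern is an inference from the stated mechanism; the protocol does not say it. If it is right, summaries of average level and average change are the wrong shape for the risk. A count of affected patients, with an interval, is the right one.

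If the case definition is left open, anyone who wants the count must take it from the listings and choose a cut-off after seeing unblinded data.

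**Working it through.** The documents give no thrombocytopenia rate, threshold or precision figure, so there is no planned figure to reproduce. The check asks what the planned outputs would show and what a patient-level rate would add.

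**Inputs from the documents**
- 50 patients planned per arm (protocol synopsis; SAP section 3.3).
- Platelet count is part of haematology, scheduled at Visits 1, 3, 5 and 6 (protocol sections 7.1 and 7.2.10).
- Numerical summaries are n, mean, SD, minimum, median, maximum and quartiles (SAP section 7.6).

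**Assumptions, not in the documents**
- A fall of 150 to 200 ×10⁹/L in each affected patient; 1 to 3 affected patients in an arm of 50.
- SD of the platelet change in other patients of 30 to 60 ×10⁹/L.

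**Step 1. Shift in the arm mean = k × fall / 50**
- 1 affected: 150/50 = 3 to 200/50 = 4.
- 3 affected: 450/50 = 9 to 600/50 = 12.

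**Step 2. Size against the noise.** With p = k/50, the shift in standard errors of a between-arm difference is shift / √[(SD² + p(1−p)·fall²)/50 + SD²/50].

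| Affected | Fall | SD 30 | SD 60 |
|---|---|---|---|
| 1 | 150 | 0.45 | 0.24 |
| 1 | 200 | 0.56 | 0.32 |
| 3 | 150 | 1.15 | 0.69 |
| 3 | 200 | 1.33 | 0.87 |

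This is only a yardstick for how visible the shift is. Neither document names a between-arm test of mean platelet change.

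**Step 3. The other planned statistics.** In a simulation of 20,000 arms of 50 (normal changes, SD 40), two falls of 200 were added:

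| Statistic | Without falls | With two falls |
|---|---|---|
| Mean | 0 | −8 |
| Median | 0 | −2 |
| SD | 40 | 56 |
| Minimum | −90 | −223 |

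The mean and median barely move. The minimum and SD react clearly, but a minimum is a single value and cannot tell one affected patient from three.

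**Step 4. What a rate would give.** Exact (Clopper-Pearson) 95% intervals for 50 patients:

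- 0/50: 0 to 7.1% (upper limit 1 − 0.025^(1/50)).
- 1/50 = 2%: 0.05 to 10.6%.
- 3/50 = 6%: 1.3 to 16.5%.

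For both Revacept arms combined, 0/100 has an upper limit of 1 − 0.025^(1/100) = 3.6%.

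**Step 5. What a rate would not give.** Against 0/50, Fisher's exact two-sided p is 0.24 for 3 cases and 0.056 for 5. It falls below 0.05 only from 6 cases (0.027). The rate would describe and bound the risk; it would not be a powered comparison.

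**The case against.** The strongest reply is that severe platelet falls would not go unseen. Several planned outputs would catch them:

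- Minimum, maximum and quartiles are standard (SAP section 7.6), and step 3 shows that the minimum responds.
- Out-of-range values are marked (protocol section 9.3.5).
- All raw data are listed by treatment group (SAP section 8.7).
- The DSMB receives unblinded laboratory values (protocol section 1.3).
- Clinically significant results, or those needing corrective therapy, are also entered as adverse events (protocol section 8.4). These are tabulated as numbers and percentages of patients (protocol section 9.3; SAP section 8.5.4).

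This stands. A reader might infer that severe falls vanish into the arm mean, or that the trial yields no thrombocytopenia rate at all. The documents support neither reading: the falls are visible by other routes, and thrombocytopenia reported as an adverse event would get a rate by arm.

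It is also fair to say that the endpoint wording names parameters and does not promise an incidence, that the study is exploratory, and that the fall sizes and SDs above are assumed.

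The reply does not supply a laboratory-defined patient rate:

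- Range marks attach to values, so one patient marked at three visits gives three marks. Because patients with counts below normal but not under 30.000/µl are not excluded by that threshold, a mark alone does not separate a new low value from an old one.
- Listings need counting by hand against a definition nobody has fixed.
- DSMB review serves monitoring and is not a reported result.
- The adverse event rate depends on investigator judgement at 16 centres using in-house laboratories, and SAP section 8.5.4 tabulates terms as reported.

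**Conclusion.** The point holds as a gap in the planned summary. Thrombocytopenia is a named endpoint without an on-study laboratory definition and without a planned per-arm number and percentage, while haemoglobin falls in the same endpoint have both cut-offs and a place in the analysis.

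The consequence is moderate. Individual falls can be found, but the report would contain no treatment-emergent, laboratory-based rate and no confidence bound on it. With 50 per arm, that bound would be 7.1% if no case occurred.

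The absence of a definition and a count rests on the documents alone. The statement that means are insensitive rests on the assumed falls and SDs; across the range tested, one to three affected patients shift the mean by 0.24 to 1.33 standard errors. The intervals assume that the planned 50 per arm all have a post-dose count, and they widen if fewer do.

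**What to change.** Before the blind is broken, add to SAP section 8.5.5, with a matching line under protocol section 9.3.5:

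- **Derived variable:** each patient's lowest post-dose platelet count, from Visits 3, 5 and 6 and any unscheduled counts recorded.
- **Table:** by arm, and for placebo against combined Revacept (the grouping already set in SAP section 8.5), the number and percentage of patients with exact 95% CI for:
  - (a) a shift from normal at Visit 1 to below the local laboratory's lower limit, using patients with a normal Visit 1 value as the denominator;
  - (b) a prespecified relative fall from Visit 1, which also covers patients who enter with low counts.
- **Listing:** patients meeting (a) or (b), with the visit of the lowest count and anti-drug antibody status.

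The sponsor should choose the cut-off in (b). It is an analysis category only and implies no clinical rule. State that the table is descriptive, and keep the planned tables as support.

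The cost is one derived variable, one table, a short listing and a stated cut-off. The scheduled counts are already collected, so no new procedure is needed.
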